3.2. Secondary Endpoint(s)

Secondary Endpoints are:

- Proportion of participants achieving improvement in different responder definitions based on assessment by sponsor-identified central pathologist(s) at Week 48 compared to baseline (each defined as above for the primary endpoint):
 - Resolution of NASH, without worsening of fibrosis
 - Improvement in fibrosis by ≥1 stage, without worsening of NASH
 - Improvement in fibrosis by ≥2 stages (defined as a decrease of at least 2 stages in the Brunt-Kleiner scale compared to baseline), without worsening of NASH
 - Improvement of ≥2 points in Total NAS (defined as a decrease of at least 2 points in Total NAS compared to baseline), without progression of fibrosis
 - Total NAS can range from 0 to 8 and is calculated as the sum of scores of steatosis (0 to 3), lobular inflammation (0 to 3) and ballooning (0 to 2). If any of the sub-scale scores are non-evaluable/missing, then the total score should be derived as missing.
- Percent change in liver fat (assessed via MRI-PDFF in substudy population), at Week 48
- Assessment of Treatment Emergent Adverse Events (TEAEs), safety-related clinical laboratory tests, vital signs, and 12-lead Electrocardiograms (ECGs), over time up to Week 48

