	collected after treatment withdrawal will be censored. • All treatment effect contrasts will be obtained through fitting the Bayesian dose-response and/or exposure-response models, or ANCOVA models	
To evaluate the effect of a range of DGAT2i doses administration of DGAT2i + ACCi, compared to placebo, and the coadministration of DGAT2i + ACCi relative to DGAT2i alone, in participants achieving improvement in different responder definitions	Using a composite estimand strategy in participants with biopsy-confirmed NASH and fibrosis, estimate the treatment effect of DGAT2i doses administered alone and coadministration of DGAT2i + ACCi relative to placebo, and coadministration of DGAT2i + ACCi, relative to DGAT2i alone, in terms of the proportion of 'clinical responders', defined as participants achieving centrally adjudicated resolution of NASH without worsening of fibrosis at Week 48 and treating all cases of withdrawal from treatment for lack of efficacy or toleration as non-responders • All treatment effect contrasts will be obtained through fitting the Bayesian dose-response and/or exposure-response models with a logit transformation, or logistic regression models • Similar estimands will be assessed for: • Improvement in fibrosis by ≥1 stage, without worsening of NASH • Improvement in fibrosis by ≥2 stages, without worsening of NASH • Improvement of ≥2 points in Total NAFLD Activity Score (NAS)	Proportion of participants achieving improvement in different responder definitions based on assessment by sponsor-identified central pathologist(s) at Week 48 − • Resolution of NASH, without worsening of fibrosis • Improvement in fibrosis by ≥1 stage, without worsening of NASH • Improvement in fibrosis by ≥2 stages, without worsening of NASH • Improvement of ≥2 points in Total NAS
To assess the safety and tolerability with a range of DGAT2i doses administered alone, and coadministration of DGAT2i + ACCi, compared to placebo, and the coadministration of DGAT2i + ACCi relative to DGAT2i alone		Assessment of TEAEs, safety- related clinical laboratory tests, vital signs, and 12-lead ECGs, over time up to Week 48
Tertiary/Exploratory:		

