To evaluate the effect of a range of DGAT2i doses administered alone, and coadministration of DGAT2i + ACCi, compared to placebo, and the coadministration of DGAT2i + ACCi relative to DGAT2i alone, on liver fat	Using a hypothetical estimand strategy, in participants with biopsy-confirmed NASH and fibrosis, estimate the treatment effect of DGAT2i doses administered alone and coadministration of DGAT2i + ACCi relative to placebo, and coadministration of DGAT2i + ACCi, relative to DGAT2i alone, in terms of the population level average percentage change from baseline in liver fat (assessed via MRI-PDFF) at Week 48, assuming all participants had remained in the trial and received treatment as planned without withdrawal up to 48 weeks. Endpoint data collected after treatment withdrawal will be censored. • All treatment effect contrasts will be obtained through fitting the Bayesian dose-response	Percent change in liver fat (assessed via MRI-PDFF in substudy population), at Week 48

Objectives	Estimands	Endpoints
	and/or exposure-response models, or ANCOVA models	
To evaluate the effect of a range of DGAT2i doses administered alone, and coadministration of DGAT2i + ACCi, compared to placebo, and the coadministration of DGAT2i + ACCi relative to DGAT2i alone, in participants achieving improvement in different responder definitions	Using a composite estimand strategy in participants with biopsy-confirmed NASH and fibrosis, estimate the treatment effect of DGAT2i doses administered alone and coadministration of DGAT2i + ACCi relative to placebo, and coadministration of DGAT2i + ACCi, relative to DGAT2i alone, in terms of the proportion of 'clinical responders', defined as participants achieving centrally adjudicated resolution of NASH without worsening of fibrosis at Week 48 and treating all cases of withdrawal from treatment for lack of efficacy or toleration as non-responders • All treatment effect contrasts will be obtained through fitting the Bayesian dose-response and/or exposure-response models with a logit transformation, or logistic regression models • Similar estimands will be assessed for: • Improvement in fibrosis by ≥1 stage, without worsening of NASH • Improvement of ≥2 points in Total NAFLD Activity Score (NAS)	stages, without worsening of NASH • Improvement of ≥2 points in Total NAS

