- Estimand 2.4: Using a composite estimand strategy, in participants with biopsy-confirmed NASH and fibrosis, as assessed by the sponsor-identified central pathologist(s), estimate the treatment effect of DGAT2i doses administered alone and coadministration of DGAT2i + ACCi relative to placebo, and coadministration of DGAT2i + ACCi, relative to DGAT2i alone, in terms of the proportion of 'clinical responders', defined as participants achieving centrally adjudicated improvement of ≥2 points on Total NAFLD Activity Score (NAS) at Week 48 and treating all cases of withdrawal from treatment for lack of efficacy or toleration as non-responders. All treatment effect contrasts will be obtained through fitting the Bayesian dose-response and/or exposure-response models with a logit transformation, or logistic regression models.
- Estimand 2.5: Using a hypothetical estimand strategy, in participants with biopsy-confirmed NASH and fibrosis, as assessed by the sponsor-identified central pathologist(s), estimate the treatment effect of DGAT2i doses administered alone and coadministration of DGAT2i + ACCi relative to placebo, and coadministration of DGAT2i + ACCi, relative to DGAT2i alone, in terms of the population level average percentage change from baseline in liver fat (assessed via MRI-PDFF) at Week 48, assuming all participants had remained in the trial and received treatment as planned without withdrawal up to 48 weeks. Endpoint data collected after treatment withdrawal will be censored. All treatment effect contrasts will be obtained through fitting the Bayesian dose-response and/or exposure-response models, or ANCOVA models.

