9.4.3. Secondary Endpoint(s)

Binary (responder) endpoints

The proportion of participants achieving resolution of NASH without worsening of fibrosis, based on assessment by sponsor-identified central pathologist(s) at Week 48 and treating all cases of withdrawal from treatment for lack of efficacy or toleration as non-responders, will be analyzed by fitting a Bayesian E_{max} dose-response model. This model will be utilized to characterize the dose response across all BID treatment groups, to estimate the proportion of responders (and 95% CI) for each BID dose studied, and to estimate the placebo-adjusted proportion of responders for each dose (and 95% CI). If the E_{max} dose-response model cannot be fitted to the data, then other models that allow dose response to be estimated will be fitted, ie, linear, log-linear or exponential. No adjustment for multiple comparisons will be made.

Similar analyses will be performed for the following secondary endpoints:

- Proportion of participants with improvement in fibrosis by ≥1 stage without worsening of NASH, based on assessment by sponsor-identified central pathologist(s) at Week 48
- Proportion of participants with improvement in fibrosis by ≥2 stages without worsening of NASH, based on assessment by sponsor-identified central pathologist(s) at Week 48
- Proportion of participants with improvement of ≥2 points on Total NAS, based on assessment by sponsor-identified central pathologist(s) at Week 48

The comparison of the proportion of responders for each of the binary secondary endpoints for DGAT2i + ACCi BID doses vs placebo as well as versus the corresponding DGAT2i BID monotherapy doses will be analyzed an using logistic regression models to estimate the proportion of responders in each treatment group and odds ratio (and corresponding 95% CI) for each treatment comparison. For comparisons of DGAT2i + ACCi BID doses vs corresponding DGAT2i BID monotherapy doses corresponding 50% CI will also be provided. No adjustment for multiple comparisons will be made.

Continuous endpoints

The continuous endpoint, percentage change from baseline in liver fat (assessed via MRI-PDFF) at Week 48, will be analyzed using a Bayesian E_{max} dose-response model for the DGAT2i BID doses.

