- Estimand 2.3: Using a composite estimand strategy, in patients with biopsy-confirmed NASH and fibrosis, on eligibility assessment of SCR2 biopsy as assessed by the sponsoridentified central pathologist(s), estimate the treatment effect of DGAT2i doses administered alone and coadministration of DGAT2i + ACCi relative to placebo, and DMB02-GSOP-RF02 5.0 Statistical Analysis Plan Template 05-Dec-2019

coadministration of DGAT2i + ACCi, relative to DGAT2i alone, in terms of the proportion of 'clinical responders', defined as participants achieving centrally adjudicated improvement in fibrosis by ≥2 stages without worsening of NASH, at Week 48 and treating all cases of withdrawal from treatment for lack of efficacy or toleration as non-responders. Participants who withdraw from treatment for other reasons but have evaluable biopsy data at withdrawal or at Week 48 will have their biopsy data assessed to determine whether they are responders or not. Participants with no Week 48 biopsy data will be considered to be non-responders. All treatment effect contrasts will be obtained through fitting the Bayesian dose-response and/or exposure-response models with a logit transformation, or logistic regression models.

- Estimand 2.4: Using a composite estimand strategy, in patients with biopsy-confirmed NASH and fibrosis, on eligibility assessment of SCR2 biopsy as assessed by the sponsor-identified central pathologist(s), estimate the treatment effect of DGAT2i doses administered alone and coadministration of DGAT2i + ACCi relative to placebo, and coadministration of DGAT2i + ACCi, relative to DGAT2i alone, in terms of the proportion of 'clinical responders', defined as participants achieving centrally adjudicated improvement of ≥2 points in Total Nonalcoholic fatty liver disease (NAFLD) Activity Score (NAS) without worsening of fibrosis at Week 48 and treating all cases of withdrawal from treatment for lack of efficacy or toleration as non-responders. Participants who withdraw from treatment for other reasons but have evaluable biopsy data at withdrawal or at Week 48 will have their biopsy data assessed to determine whether they are responders or not. Participants with no Week 48 biopsy data will be considered to be non-responders. All treatment effect contrasts will be obtained through fitting the Bayesian dose-response and/or exposure-response models with a logit transformation, or logistic regression models.

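### Protocol and SAP define Estimand 2.4 differently: the SAP adds a no-fibrosis-worsening condition, and no SAP responder analysis covers the protocol's NAS endpoint

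*SAP*

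**What the plan says.** The protocol states this endpoint in four places, each without a fibrosis condition. The synopsis (1.1) lists "Improvement of ≥2 points in Total NAS", and the objectives table in Section 3 has "Improvement of ≥2 points in Total NAFLD Activity Score (NAS". Estimand 2.4 in Section 9.1.1 counts as responders those "defined as participants achieving centrally adjudicated improvement of ≥2 points on Total NAFLD Activity Score (NAS) at Week 48". Section 9.4.3 lists "Proportion of participants with improvement of ≥2 points on Total NAS, based on assessment by sponsor-identified central pathologist(s) at Week 48" among the binary secondary endpoints that are to receive the Emax dose-response and logistic regression analyses.

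The SAP keeps the number 2.4 but changes the variable. SAP 2.1.2 requires an improvement of "≥2 points in Total Nonalcoholic fatty liver disease (NAFLD) Activity Score (NAS) without worsening of fibrosis at Week 48". SAP 3.2 gives the endpoint as an improvement "defined as a decrease of at least 2 points in Total NAS compared to baseline), without progression of fibrosis". The title of SAP 6.2.4 and the matching row of Appendix 1 repeat the fibrosis condition.

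On authority to change the plan, Protocol 9 and SAP 2 both allow the SAP to depart from the protocol. They promise a protocol amendment only for major changes to the primary endpoint or its analysis.

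**The concern.** One estimand number stands for two different variables. A participant whose Total NAS falls by 2 or more points while fibrosis rises by a stage is a responder under the protocol and a non-responder under the SAP. If the SAP is followed, the result reported as Estimand 2.4 does not estimate what the protocol says it estimates, and the protocol's own endpoint has no planned estimate.

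The two versions answer different questions. Protocol 4.2 asks whether an effect on liver fat carries through to histology. Total NAS includes steatosis (SAP 3.2), so improvement in NAS alone and improvement in NAS with fibrosis held are separate steps in that argument. A reader who compares the study report with the protocol would find a changed secondary outcome under an unchanged label.

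**Working it through.** No figure in the plan bears on this point, so the check is a comparison of text followed by the logic of the two definitions.

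**1. The definitions side by side**

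| Place | NAS requirement | Fibrosis requirement |
|---|---|---|
| Protocol 1.1 and 3 | fall of ≥2 points | none |
| Protocol 9.1.1, Estimand 2.4 | fall of ≥2 points | none |
| Protocol 9.4.3 | fall of ≥2 points | none |
| SAP 2.1.2, Estimand 2.4 | fall of ≥2 points | no worsening |
| SAP 3.2 | fall of ≥2 points | no progression |
| SAP 6.2.4 and Appendix 1 | fall of ≥2 points | no worsening |

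The difference does not look like a slip on either side. In the protocol's lists the other three histological secondary endpoints each carry an explicit no-worsening qualifier, and this one does not. In the SAP the qualifier appears every time.

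**2. Are the SAP's two wordings the same?** Yes. SAP 3.1 defines no worsening of fibrosis as a stage that is unchanged or lower, and SAP 3.3 defines progression as an increase of at least one stage. Absence of one is absence of the other.

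**3. Does any other SAP analysis supply the protocol's version?**
- The summary, main and sensitivity rows for this endpoint in Appendix 1 all sit under the conditioned definition.
- The other endpoints in SAP 3.3 include versions free of the second component for fibrosis improvement, fibrosis progression and NAS worsening. There is none for NAS improvement.
- The shift tables in SAP 6.1.1.2 are by individual NAS component and by fibrosis grade. They do not yield Total NAS responders, nor the model estimates that Protocol 9.4.3 promises.

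**4. How the two rates relate.** For arm k, let p be the protocol response rate. Let a be the share who are protocol responders with a fibrosis increase of at least one stage. Let b be the share who are protocol responders but whose Week 48 fibrosis is not evaluable and has no repeat read to substitute. The group b arises because SAP Table 10 makes a participant a non-responder when a component required for the endpoint cannot be read, and fibrosis is required only under the SAP's version. Then

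- SAP rate: s_k = p_k − a_k − b_k
- SAP difference: s_T − s_C = (p_T − p_C) − [(a_T + b_T) − (a_C + b_C)]

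So the SAP rate in any arm is at most the protocol rate. The difference between arms may shrink, stay the same or grow, depending on which arm loses more responders. The documents give no value for p, a or b.

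**The case against.** The strongest reply is that the SAP is entitled to do this. Both documents let it modify the protocol, and a secondary endpoint falls outside the amendment promise. That stands: no stated rule is broken. The permission does not, however, make the two definitions agree, and the SAP's endpoint and analysis sections neither give a reason nor renumber the estimand.

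The consequences are also limited, and that stands too. No formal hypothesis tests are planned (Protocol 9.1.2, SAP 5.1), there is no multiplicity adjustment, and the sample size rests on the primary endpoint (Protocol 9.2).

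Third, the stricter version cannot raise any arm's response rate, and it matches the form of the other three histological secondary endpoints. Both are true. A reader might infer that it is therefore conservative for the treatment effect. The second formula shows that this does not follow.

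Fourth, planned outputs partly bound the gap. Everyone in group a has fibrosis progression, which the SAP reports by arm, so that count caps a. The cap must come from the observed-data summary in Appendix 1, because the main analysis of progression counts dropouts as having worsened. It does not cap b, and a bound does not replace the planned estimate.

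A reader might also infer that the endpoint was replaced silently. The documents do not support that. The SAP change log available here starts part-way through its newest entry, so a line recording this change may sit in the missing part.

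**Conclusion.** The mismatch is real, and it rests only on the text: same estimand number, different responder definition, and no SAP responder analysis of the protocol's version. It is an unreconciled definition in an untested secondary endpoint. It should be settled, but it does not touch the primary endpoint, the sample size or error control.

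Its size cannot be stated. A reader might reach for an example: with an assumed 40% protocol response rate, and an assumed 5% to 15% of those responders progressing in fibrosis, the SAP rate would be 0.40 × 0.95 = 38% down to 0.40 × 0.85 = 34%. Neither input comes from the documents, and the example describes a single arm and says nothing about the treatment difference, so no weight should be put on it.

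A reader might also infer that the SAP's version is the wrong one and must be demoted. The documents do not show that. Either version could be the secondary endpoint, provided both documents say the same thing.

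**What to change.** - Add to the SAP a responder analysis of at least a 2-point fall in Total NAS at Week 48 regardless of fibrosis change, with the same composite strategy and the same Bayesian Emax and logistic models, and a matching row in Appendix 1. For this version, only the NAS components should count as required under SAP Table 10.
- Give the two versions distinct estimand numbers.
- State which version is the secondary endpoint and why, and align the protocol and SAP wording accordingly. If the conditioned version is kept as secondary, record the departure from the protocol and its reason.
- Use one term, either worsening or progression, throughout the SAP.

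Cost: one extra run of existing code and wording changes, best made before unblinding. Total NAS is already derived under SAP 3.2 and the biopsy readings are already collected, so no new data are needed.

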3.3. Other Endpoint(s)

- Proportion of participants achieving improvement in fibrosis by ≥1 stage independent of changes in NAS, based on assessment by sponsor-identified central pathologist(s), at Week 48 compared to baseline
- Proportion of participants achieving resolution of NASH without worsening of fibrosis
 and improvement in fibrosis by ≥1 stage without worsening of NASH, based on
 assessment by sponsor-identified central pathologist(s), at Week 48 compared to baseline

- Proportion of participants with worsening in liver biopsy endpoint components based on assessment by sponsor-identified central pathologist(s) at Week 48:
 - Progression of fibrosis by ≥1 stage (defined as an increase of at least 1 stage in the Brunt-Kleiner scale compared to baseline) independent of changes in NAS
 - Progression of fibrosis by ≥1 stage and worsening of ≥2 points in Total NAS
 - Worsening of ≥2 points in Total NAS (defined as an increase of at least 2 points in Total NAS compared to baseline) independent of changes in fibrosis

Other tertiary/exploratory endpoints are as shown below. The analyses of these endpoints are assessed for efficacy up to Week 48, but the analyses of blood based biomarkers will also include data up to and including Week 50 to allow an assessment of off-treatment effects::

- Percent change in liver fat (assessed via MRI-PDFF in Imaging substudy population), over time up to Week 48
- Percent change in liver volume (assessed via Magnetic resonance imaging (MRI) in Imaging substudy population), over time up to Week 48
- Percent change in CCI (assessed via MRI in Imaging substudy population), over time up to Week 48
- Percent change in CCI (assessed via MRI in Imaging substudy population), over time up to Week 48
- Percent change from baseline in liver fat as assessed via Controlled attenuation parameter (CAPTM) measure by FibroScan[®], (entire study population), over time up to Week 48
- Percent change from baseline in liver stiffness (assessed via Vibration-Controlled Transient Elastography (VCTE™) using FibroScan® (entire study population)), over time up to Week 48
- Percent change from baseline in Liver Function Tests Alanine aminotransferase (ALT), Aspartate aminotransferase (AST), Alkaline phosphatase (ALP), Gamma-glutamyl transferase (GGT), Total Bilirubin, Direct Bilirubin, and Total Bile Acids over time up to Week 50
- Percent change from baseline, overtime up to Week 50 in Mechanism-Related and Metabolic Parameters – Proprotein convertase subtilisin/kexin type 9 (PCSK9), Adiponectin, Platelet count, eGFR-CKD-EPI-Cystatin-C, and Body Weight
- Percent change from baseline, overtime up to Week 50 in Cytokeratin-18-M30 fragment (CK18-M30) and Cytokeratin-18-M65 fragment (CK18-M65)

- Percent change from baseline, overtime up to Week 50 in N-terminal propeptide of type III procollagen (ProC3) and C-terminal fragment of α3 chain of procollagen type VI (ProC6)
- Percent change from baseline, overtime up to Week 50 in Enhanced Liver Fibrosis (ELF) score (including the individual parameters assayed Serum hyaluronic acid (HA), Serum amino-terminal propeptide of type III procollagen (PIIINP) and Serum tissue inhibitor of metalloproteinases 1 (TIMP-1))
- Percent change from baseline, overtime up to Week 50 in High-sensitive C-reactive protein (hs-CRP)
- Percent change from baseline, overtime up to Week 50 Apolipoprotein A1, B (total), B100, B48, C3, E (Potentially mechanism-related parameters)
- Percent change from baseline, overtime up to Week 50 in Fasting lipid panel (total cholesterol, direct Low density lipoprotein-cholesterol (LDL-C), High density lipoprotein cholesterol (HDL-C), triglycerides, direct Very low-density lipoprotein (VLDL)),
- Change from baseline, overtime up to Week 50 in HbA1C, Fasting plasma glucose (FPG), Fasting plasma insulin (FPI), Homeostatic Model Assessment for Insulin Resistance (HOMA-IR)
- Change from baseline, (adults with T2DM only), over time up to Week 50, in HbA1C, Fasting plasma glucose (FPG), Fasting plasma insulin (FPI), Homeostatic Model Assessment for Insulin Resistance (HOMA-IR)
- Change from baseline, over time to Week 48 in abdominal pain and bloating questions from the NASH Symptom Diary
- Change from baseline, over time to Week 48 in fatigue, sleep disturbance, and daytime sleepiness questions from the NASH Symptom Diary
- Change from baseline, over time to Week 48 in fatigue as measured by Patient-Reported Measurement Outcome Information System (PROMIS) Fatigue questionnaire
- Change from baseline, over time to Week 48 in Health-related quality of life (HRQoL) sub-scale scores as measured by NASH-Check
- Change from baseline, over time to Week 48 in PGI-S
- Absolute score over time in Patient Global Impression of Severity (PGI-S)
- Absolute score over time in Patient Global Impression of Change (PGI-C)

